## **VI. Data Security and Confidentiality Protections:**

### **a. Personally Identifiable Information (PII):**

Please identify the Personally Identifiable Information (PII) that you may be collecting and using at any of the following stages of your study: ***Recruitment, Consent, and Study Implementation.***

Name, signature, initials, or other identifiable code	
Geographic identifier: address, GPS location, etc.	
Dates: birth, death, clinical service, discharge, etc.	
Contact information: phone numbers, email address, etc.	
ID: Social Security Number, driver's license number, etc.	
Health record identifiers: medical record, insurance plan number, etc.	
Account numbers	
Device identifiers: e.g., implants	
Internet identifiers: IP address, social media accounts	
Biometric identifiers, including finger and voice prints	
Audio recordings	
Video or full face photographic images	
Genomic/genetic data	
Any other unique identifying number, characteristic, or code (note: this does not mean the unique code assigned by the investigator to code the data)	
Other: Click here to enter text.	

### **b. Recruitment:**

Will you collect identifiers for the purpose of contacting potential participants? Yes  No

If **yes**, will you retain the identifiers after the recruitment contact has been made? Yes  No

### **c. Data Collection:**

Collection of data for a research study can take on many forms. It can be as simple as gathering the data with pen and paper or developing an on-line adaptive survey that changes based on the participant's answers. Regardless of the method, PII for the purposes of identifying the participants will

most likely be collected. Once collected, the raw data should go through a de-identification process to further protect PII.

In what form will you collect and store PII? When you respond, think of PII collected for recruitment, consent, and other study purposes.

a. **Hard Copy/Paper:** Yes  No

If yes, please answer the following:

1. How will the data be kept secure during transfer from study collection site to storage site?

All data collected on paper forms will include only the participant's ID number. Paper forms will be transferred securely in study vehicles to the storage site where they will be kept in locked filing cabinets within locked offices.

2. Will the data be secured in a locked cabinet or room? Yes  No

3. If study IDs/Codes are used, will they be stored separately from the study data? Yes  No

4. Will the hard copy/paper be destroyed after data abstraction and cleaning are complete?  
Yes  No

If No, when do you plan to destroy the hard copies?

b. **Electronic:** Yes  No

If yes, please answer the following:

1. Will the data be collected/stored on a portable device (laptop, mobile phone, tablet, PDA) protected by encryption? Yes  No

2. Will study participants use personally owned devices or study-provided devices?  
Personally owned  Study provided

3. Is the application/website used for data collection being developed in-house (Hopkins) or by a 3rd party vendor?

In-house  3rd party

If 3rd party, provide the name of vendor and URL:

Identify Mobile Ecosystem (check all that apply) Apple  Google  Website

Tufts University: <http://medicine.tufts.edu/Education/Academic-Departments/Clinical-Departments/Public-Health-and-Community-Medicine/Nutrition-and-Infection-Unit/Research/Implementation-Science/ACASI-CASI-CAPI>

4. Will the data be stored on a secure server (@JHSPH/on-site)? Yes  No

5. Will the data be stored in the Cloud/Web? Yes  No
6. Will it be encrypted? Yes  No
7. Will you be backing up your data? Yes  No

c. **Audio Recording:** Yes  No

If yes, please answer the following:

1. Will you store the audio recording securely in a locked cabinet/room until transcription is complete?  
Yes  No
2. Will you use a transcription service?  
Yes  No   
If yes, if the PII comes from JHH/JHHS, you must use an approved vendor; otherwise, be aware of the data security protections that the transcription service provides.
3. Will the audio recording be destroyed after transcription? Yes  No

If no, why not?

• **Photograph/Video:** Yes  No

If yes, please answer the following:

1. Will the photographs/videos be stored securely in a locked cabinet or room? Yes  No
2. Will the photograph/video be destroyed? Yes  No

If yes, when?

d. **PII De-Identification of Data Used for this Study:**

1. When will you destroy the PII and/or the code linking the PII with the study ID? PII will be destroyed immediately following the end of the participant's participation in the study (i.e., following the last study visit with the participant when their contact information will no longer be needed)
2. What is the method you will use to de-identify the data? All PII will be stripped from datasets. Only a unique ID number will be included in de-identified data.
3. Is your research data governed by HIPAA (U.S. clinical data remaining within the covered entity)?  
Yes  No
1. If yes, who is doing the de-identification?
2. If yes, what level of de-identification will you achieve (Limited data set? De-identified?)

e. **Data Storage and Analysis:**

One of the keys to protecting PII is the proper use of tools to share and conduct your analysis. JH and JHSPH offers several options for you to consider. Please select the system that you plan to use to protect your study data by clicking the box. Consult JHSPH IT for assistance if needed.

- JH Virtual Desktop**: The Hopkins Institute for Clinical and Translational Research (ICTR) provides a virtual Windows desktop (SAFE Desktop). It includes productivity software such as Microsoft Word and Excel, as well as statistical software, including SAS, Stata, R, R Studio, and Python. 100 GB of storage space is provided.
- JHSPH SharePoint and File Shares**: These systems provide a managed and secure platform for your research project. They also provide a built-in encrypted backup solution.
- JHSPH RedCAP**: These are departmentally managed applications. RedCAP is an application designed for collaborative research projects.
- JHSPH HPCC**: High Performance Computing Cluster (HPCC: <https://jhpce.jhu.edu/>) can provide the high capacity computing required for very large data sets.
- JHBox**: Johns Hopkins Box (JHBox) is a secure cloud-based file sharing service which enables people to collaborate and share information and may be accessed through any device: desktop, laptop, phone, or tablet with appropriate permissions. JHSPH IT recommends that investigators not use JHBox as a primary storage location, but use it instead for initial data collection, sharing results, and other collaborative information with the research team.
- Independent Departmental Servers and Systems**: These servers are typically managed by departmental or research team IT staff. Because these servers are not centrally managed by JHSPH IT, all documentation regarding data security protections will need to be provided by the owner/administrator of the server. This responsibility may fall to the data owners (PI).
- Other**: Please provide details regarding any other systems being utilized. Examples may include servers and applications located at another university participating in your study or a 3rd party web-based application. Data will be securely stored on CIDRZ DHIS-2 server, which is used for all of their HIV clinical programming. Access to the server is restricted to only essential personnel. Data are encrypted. Only the data manager at CIDRZ and [name] will have access to data for this project. [name] will have secure access to the server remotely through a VPN.

f. **Other Data Security Measures**:

In addition to the details regarding data collection, please review the following questions. This additional information will be utilized to assist in the development of a comprehensive Data Security plan. This would include the systems used to analyze the data, data security contacts and additional requirements.

- a. During the analysis phase, do you plan to use computer systems that are not managed by JHSPH or JH? Yes  No

If yes, please explain:

- b. Do you have a designated person on your research team other than the PI who is the technical contact for a Data Security plan? Yes  No

If yes, please provide a contact name:

1. Does your sponsor have other specific data security requirements for the study data? Yes  No   
If possible, please explain:

c. Please add any other information that you believe is relevant to data security.

**g. Certificate of Confidentiality:**

All NIH studies include Certificate of Confidentiality protections with the grant; the consent form must include the C of C language provided in our template. Other funders may obtain C of C protections through NIH. (<https://humansubjects.nih.gov/coc/index>)

Does the study have Certificate of Confidentiality protections?

Yes  No

**h. JHM Clinical Records:**

Will you use clinical data of 500 records or more from Johns Hopkins Hospital and its affiliates?

Yes  No

If yes, please complete the JHM Data Security Checklist available on the JHSPH IRB website: [www.jhsph.edu/irb](http://www.jhsph.edu/irb) and upload a copy of the checklist to the "Miscellaneous" section.

**VII. Risks of the Study:**

- Describe the risks, discomforts, and inconveniences associated with the study and its procedures, including physical, psychological, emotional, social, legal, or economic risks, and the risk of a breach of confidentiality. These risks should be described in the consent documents.

Risk associated with the study include:

- Emotional distress, resulting from assessment measures or therapy sessions
  - Risk of breach of confidentiality, including stigmatizing conditions such as HIV and alcohol use disorder
- Describe the anticipated frequency and severity of the harms associated with the risks identified above; for example, if you are performing "x" test/assessment, or dispensing "y" drug, how often do you expect an "anticipated" adverse reaction to occur in a study participant, and how severe do you expect that reaction to be?

Based on previous studies by our team in Zambia with similar study populations and trial designs, we expect the frequency of harms to be low and the severity to be minor.

- Describe steps to be taken to minimize risks. Include a description of your efforts to arrange for care or referral for participants who may need it.

Study staff and peer educators will be trained in responding to distress and multiple levels of back-up support have been developed. Assessors and study staff are encouraged to contact the clinical supervisors and/or [name] [name] who are extensively trained in clinical matters such as identifying levels of distress, local referral options and processes, and clinical interviewing on sensitive topics. We will also have a safety protocol that has been developed in collaboration with the University of Zambia, University Teaching Hospital, CIDRZ, and the Ministry of Health which includes: a) immediately contacting a clinical supervisor, b) the supervisor guiding them through additional questions and help make a decision if the participants needs to be brought to see a specialist, if they need to do an immediate home visit, or if a 1-day safety contract may be completed, c) [name] [name] and [name] will be contacted immediately by the supervisor to further assess and give

recommendations, and d) MPIs Drs. [name] and [name] and [name] (clinical co-I lead) and will be contacted within 24 hours and notified of the situation.

#### i. Emotional distress

Assessments and Intervention: Participants will receive questions each week during the intervention phase to assess suicide and homicide risk (in person for CETA participants during their session; via phone for BI participants). A primary outcome of the proposed study is retention in CETA. Therefore, we want to minimize research contacts with participants as much as possible. We must balance that research aim, however, with the need to clinically monitor our study participants for safety. If a participant in the pilot RCT indicates high risk, their counselor will immediately follow the locally developed safety protocol above. In the BI control arm, if the participant does not respond within 24 hours to the phone contact, a counselor will do a home visit to assure response to safety questions. All assessors will be trained in how to recognize and respond to distress that may occur during the intervention, and will call their supervisor if they are unsure. At least one member of the clinical study team ([name], [name], [name], Zambian clinical supervisors) will be on-call at all times to address any urgent cases.

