CBT for alcohol and other substance use	CBT and MI integrated element to set goals and reduce use; Identification and strategies for addressing drivers of use	Reduce alcohol/substance use Increase social support
Behavioral Activation	Identify and engage in pleasurable activities	Reduce depressive symptoms; Facilitate engagement in helpful programs
Cognitive Coping/Restructuring	Identify and correct thoughts, feelings, and behaviors Replace unhelpful thoughts with helpful ones	Reduce depressive, anxious, and trauma-related symptoms; Reduce self-blame and stigma; Reduce negative thoughts on HIV care
Relaxation	Breathing exercises, imagery	Reduce anxiety and stress-related symptoms
Exposure	Talk about trauma memories or confront fears using gradual desensitization	Reduce trauma and anxiety symptoms
Problem Solving	Teach a process of steps to solve problems and make healthy decisions	Promote health decision making Skills training for problem solving

CETA will be delivered within the clinic with an option for community-based delivery (i.e., in a local church or community center) if preferred by the participant, similar to previous Zambia studies. To estimate uptake of CETA in a “real-world” HIV clinic setting, if participants do not attend their initial meeting, counselors will make several phone follow-ups for up to a maximum of 1 month after enrollment. If the participant does not start treatment within one-month post-enrollment, the counselor will cease efforts to engage them in CETA as additional retention efforts would be impractical in a non-research setting. After the initial session, if a client misses a follow-up appointment, the counselor will again follow-up by phone up to three times in a week and make a one-time home visit to re-engage the client. The research team will not contact the participant during the active intervention phase so as not to artificially influence the participant to attend CETA sessions.

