[Tracking of treatment uptake and completion.](#) We have developed rigorous and sophisticated participant tracking systems through our previous Zambia studies. We will systematically track throughout the course of the study: (1) the number of participants who successfully complete and decline BI; (2) the number of participants who successfully link to CETA, defined as attending the first CETA session; (3) the amount of time counselors dedicate to client tracking/retention; and (4) the number of clients who successfully complete CETA. Counselors will attempt to track clients to the extent that this would be practical in a real-world setting.

[Clinical monitoring data collection.](#) During CETA sessions, the counselor will administer a brief clinical symptom checklist (Client Monitoring Form; CMF) and a past 7-day Alcohol TLFB. These data guide clinical care by informing the choice of CETA elements to be delivered in session and will also be used in analyses. These forms will only be administered to CETA participants during their CETA sessions. (Neither RCT participants randomized to the BI alone nor Cohort study participants will complete the TLFB).

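### The weekly suicide and homicide questions have no stated route for CETA participants in a week without a session

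*Combined protocol and SAP*

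**What the plan says.** Emotional distress (under VII. Risks of the Study) makes a general commitment: "Participants will receive questions each week during the intervention phase to assess suicide and homicide risk". It gives the mode by arm: "in person for CETA participants during their session; via phone for BI participants". One rule for a missed check follows. It opens "In the BI control arm, if the participant does not respond within 24 hours to the phone contact", and has a counselor visit the home to get the questions answered. Another sentence sends the counselor to the safety protocol when a trial participant indicates high risk, which presupposes that the participant has been asked. The same paragraph calls retention in CETA a primary outcome, gives that as the reason to keep research contacts few, and adds: "We must balance that research aim, however, with the need to clinically monitor our study participants for safety".

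Interventions (under V. Study Procedures) describes CETA as weekly sessions over 6–12 weeks, and the BI as one session of 10–15 minutes on the baseline day. For a CETA participant who misses the first meeting, "counselors will make several phone follow-ups for up to a maximum of 1 month after enrollment". Then: "If the participant does not start treatment within one-month post-enrollment, the counselor will cease efforts to engage them in CETA". After a later missed session, the counselor phones at most three times within a week and will "make a one-time home visit to re-engage the client". The research team makes no contact while the intervention is active. On the symptom checklist and drinking record used in CETA, the plan says: "These forms will only be administered to CETA participants during their CETA sessions".

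**The concern.** The RCT takes people with moderate-to-severe alcohol use disorder, or with scores above set thresholds for depression, trauma or other substance use. Active suicidality is an exclusion at entry, but that does not cover later change. The adverse-event section itself anticipates suicidal and homicidal ideation and clinical worsening. The steps for removing a participant and arranging psychiatric care work only if someone detects the problem.

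In the BI arm the weekly check does not depend on attendance: the participant is phoned, and visited if there is no reply. In the CETA arm the only stated check is tied to attendance. A participant who stops CETA because of distress therefore loses the stated check at that moment. There is also an ascertainment issue. If the arms differ in how often the questions are asked, adverse-event counts by arm are not fully like for like.

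**Working it through.** The plan states no figure on this point, so the check sets each situation in the intervention phase against the contacts that the plan specifies.

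| Situation that week | Stated route for the safety questions | Stated rule if the check is missed | Other stated contact |
|---|---|---|---|
| BI control arm | Phone | Home visit after 24 hours without reply | None needed |
| CETA, attends session | In session | Not needed | Session content, symptom checklist |
| CETA, not yet started | None | None | Several engagement calls, 1 month at most |
| CETA, misses a session | None | None | Up to three calls in a week, one home visit |
| CETA, has stopped | None | None | As for a missed session, then nothing |

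**Possible back-up routes.**
- The Safety element in the CETA component table and the symptom checklist are both delivered in sessions, so they lapse with attendance.
- On-call clinical staff (Emotional distress) and clinical-team oversight (X.C Safety Monitoring) have no contact schedule for non-attenders.
- The next study assessment for everyone is at 6 months.
- CETA non-attenders have still been offered the BI and remain in usual HIV care. Neither is said to include the weekly questions.

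**Number of people.** The CETA arm has 80 participants (Interventions). The plan gives no rate of never starting. The 20% in the sample-size section is loss to follow-up or drop-out, a different quantity. With an assumed share u never starting, the number is 80 × u:
- u = 0.10: 80 × 0.10 = 8
- u = 0.20: 80 × 0.20 = 16
- u = 0.40: 80 × 0.40 = 32

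These people would have no specified check at any time in the intervention phase. Those who start and then stop or miss sessions come on top; the documents give no basis for counting them.

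**Length of time.** The plan does not define the intervention phase. The BI is a single session, so it sets no length. Taking one month as about 4 weeks, a CETA course begun at the latest permitted point and run for 12 weeks ends at about 4 + 12 = 16 weeks. For a non-starter, the weeks beyond the engagement calls are 0 if the phase ends when those efforts cease, 6 − 4 = 2 if it lasts 6 weeks, and 12 − 4 = 8 if it lasts 12. That spread follows from the missing definition, so totals in participant-weeks would not be informative. The gap does not depend on which reading is right: even within the first month, the calls are not stated to carry the questions.

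**The case against.** **The commitment covers everyone.** The sentence promising weekly questions speaks of participants without restriction, and the bracket may give only the usual mode. Detail may also sit in the adapted CETA procedures, the safety protocol or the adverse-event procedures sent to the DSMB, none of which is in this document. This stands as to intent. A reader might infer that the sponsor chose to leave CETA non-attenders unmonitored; the documents do not support that. They do show a text that, if followed literally, provides no check.

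**Contact is capped, not absent.** The limits are deliberate, to estimate uptake in real-world conditions. A reader might take the gap to mean no contact at all, and that would be wrong: there are calls, a home visit and on-call clinical cover. None is stated to include the questions.

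**All participants receive a BI, so the phone route might cover both arms.** This fails. The bracket contrasts CETA participants with BI participants, and the missed-check rule names the BI control arm.

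**The DSMB is not blind to non-attendance.** A reader might infer that a missing check would leave no trace. That goes too far: the Stage 1B overview commits to capturing uptake, attendance, completion and clinical-monitoring data, and DSMB reports cover attrition. Attendance shows which CETA weeks had no session. What is unstated is a record of the checks themselves, in either arm.

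**More calls may distort retention.** This stands. Weekly calls to non-attenders could prompt some to attend, and retention in CETA is called a primary outcome.

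**Conclusion.** The gap is real and should be closed. Weekly suicide and homicide questions are promised, but a CETA participant without a session that week has no stated route to them and no stated rule for the missed check, while a BI participant has both. This is more than a missing detail, because staff who follow the text would screen the two arms differently.

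The size is unknown. The figure of 8–32 of 80 rests wholly on the assumption that 10–40% never start CETA, and it leaves out those who stop or miss sessions. No estimate of missed events can be made from the documents, and none is implied. The point concerns participant safety and adverse-event ascertainment; the sample size and the primary AUDIT analysis are unaffected.

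**What to change.** 1. In Interventions and in Emotional distress, require the counselor to ask the suicide and homicide questions at every non-attendance call and home visit already planned. This adds no contacts.

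2. In Emotional distress, define one safety-check period, counted from randomisation and the same in both arms. In-session checks continue for anyone still in CETA after it ends; this matters because a late start can carry a course to about week 16. In any week of the period when a CETA participant who has not completed treatment has neither a session nor an answered check, apply the existing BI rule: a counselor phones, then visits if there is no response in 24 hours. Use a safety-only script that does not mention attendance. Completers are left out because they are not in the gap.

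3. Record checks done and missed by arm, and show them beside the adverse events in the six-monthly DSMB reports.

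Part 2 costs some short calls and home visits by existing counselors; how many depends on uptake and on the period chosen, which the documents do not give. It may also nudge CETA attendance slightly and so affect the retention outcome. The script limits that effect but does not remove it. The plan already accepts that few contacts must be weighed against safety monitoring.
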